7.7.6.3. Multivariate/Adjusted Analysis

Hazard ratios will be estimated, using Cox proportional hazards models, to explore the risk of first occurrence each safety endpoint in women newly exposed to *Duavee* when compared to initiators of E+P HRT, adjusted using propensity score matching.

7.7.7. Multiplicity Issues

This study will examine a number of end points, which introduces the possibility of incorrectly identifying a significant association between *Duavee* exposure and a given outcome. In order to minimize the effect of multiple endpoints, two primary endpoints, endometrial hyperplasia and endometrial cancer have been identified.

Otherwise, multiple comparisons will not be addressed in the analyses. Further, the primary purpose of this study is estimation of IRs and HRs, and not testing of hypotheses.

7.7.8. Missing Data

The distribution of all variables will be examined to determine the presence of outliers. Patients with implausible values for age (eg, age >120 years) or multiple values for gender will be regarded as having missing data for these variables and excluded from the analyses; the number of potential individuals excluded due to these data integrity issues will be described and is expected to be small. Imputation or other adjustments for missing values are not planned.

7.7.9. Layout of Results Tables

Table shells showing how study results will be presented are contained in [Annex 1](#).

7.8. Quality Control

HealthCore's research team documents the progress and scientific and quality review of all study activities and deliverables (e.g., protocol, data management, data analysis, reports, manuscripts, etc) in a Project Log. The Project Log provides documentation of the major study tasks related to a specific study activity performed by HealthCore to develop and execute the requirements of the protocol. In addition, the Project Log documents the quality assurance measures performed for each study activity during the conduct of the study. Any change to study specifications (e.g., protocol, study database, variables in the analytic files, etc) is also described in the Project Log. This is necessary to ensure that such communications are appropriately documented, that the most up to date versions of relevant documents are readily identifiable, and that affected documents are clearly tracked in the Project Log.

All programming required for study database extraction and creation of the analytic datasets from the HIRD will be performed in accordance with HealthCore Programming Standards.

The HealthCore Programming Standards are a set of documents describing data extraction methods that are referenced in HealthCore SOPs and provide a guideline for basic, frequently used terms and definitions and respective coding information to maintain operational consistency. Data validation will occur throughout the data management and analysis process. Data quality checks include, but are not limited to, programming checks by an individual who is not main programmer for the study, internal dataset consistency, and checks to ensure that Protocol criteria were met. If validation checks are not satisfied then an examination of the problem will be performed on the dataset or datasets in question and the problem resolved. All data validation, quality checks, and resolution of issues identified will be documented in the Project Log.

To help ensure consistency of clinical data collection from medical records, the medical record vendor will be trained on the study's process for medical record acquisition as agreed by HealthCore and Pfizer and approved by an Institutional Review Board (IRB). As part of the training, a pilot phase will be conducted to review a sample of charts (i.e., 5-10 charts) to help ensure that the trained professionals are accurately collecting the data. If any themes are identified across the trained professionals that are resulting in errors in medical record acquisition, re-training may be requested by HealthCore. Throughout the entire medical record acquisition phase, the vendor will keep a question log that will be transferred back and forth with HealthCore. This log will allow the vendor to ask any questions that may not have come up during the training and give HealthCore the opportunity to provide standard answers that will then be shared with the vendor's trained professionals. HealthCore will perform quality checks on the clinical data obtained from the medical records, including any assessments of the clinical data by clinical consultants with expertise in endometrial disease, and resolve any errors or discrepancies. HealthCore will integrate the clinical data with the claims analytical file from and HIRD and perform quality checks to ensure all the variables for analysis are correctly included.

7.9. Strengths and Limitations of the Research Methods

Strengths:

- This PASS uses population-based data sources of the real-world actual use of *Duavee*. These data will record use in a population anticipated to be broader than the indication for which *Duavive* is authorized in the EU and will complement the existing clinical safety data for CE/BZA. Unlike spontaneous reporting data, the incidence of safety endpoints can be estimated. The HIRD is a well-established resource for conducting pharmacoepidemiologic research and has been shown to be nationally representative with good validity in capturing patient care.^{1,2,3,4}
- The results of this US PASS will apply to the EU population expected to initiate treatment with *Duavive*. The PASS will provide insight into any possible association of *Duavive* use and the targeted safety events in the EU population. This is true because the internal validity of this study will be optimized, due to careful attention given to designing a study that isolates any true biological relationship between *Duavive* and safety risks, from differences in risk arising from bias due to selection, confounding, or

other sources of error. See [Section 7.10](#) for further discussion of the generalizability of this US PASS to the EU.

- Many of the endpoints in this study are well-defined in US healthcare data and have been studied in pharmacoepidemiology studies,^{13,14} some in reference to HRT.¹⁴ Further, MI, and stroke endpoints have been confirmed to have a high PPV in HIRD validation studies.¹
- HIRD has the capability to conduct linkage with the US NDI, and offers access to medical records for validating algorithms to identify events of endometrial hyperplasia (eg, from biopsy results) and endometrial cancer.
- HIRD is among the very largest longitudinal healthcare databases in the US. The projection of study size indicates that meaningful elevated risks can be both detected and excluded.

Limitations:

- Use of administrative healthcare data for research is associated with outcome misclassification, due to missing codes or coding errors, or to limits in the time period of patient observation available in the data. This study will use well-established sources, but misclassification may still be present. Specifically, women who have had a hysterectomy before their baseline 12 month period and started either *Duavee* or E+P HRT would be misclassified as having an intact uterus. However, this misclassification would be non-differential and would not bias the study comparison.
- There may be uncontrolled residual confounding aspects due to unmeasured prescribing factors that differ between the *Duavee* and E+P HRT patient cohorts. Physicians prescribe drugs for specific medical reasons and this may introduce channeling biases whereby one cohort is at higher risk for a particular safety event. This bias could also be due to unrecorded cardiovascular and cancer risk factors such as smoking, body mass index (BMI), and family history. Because the analyses rely on automated claims collected primarily for billing purposes, some desirable data elements are not captured. Lifestyle factors such as smoking and biometric measures like BMI, for example, are systematically unavailable. Likewise, family history of endpoints is unknown. These factors present another source of residual confounding.
- Despite the large size of the HIRD, the identified safety endpoints are rare events so there will be a limit to the precision with which it can estimate elevated risks associated with *Duavee* use. Additionally, the cancer endpoints may have long latency periods from exposure and the ability to follow patients long-term will be limited by duration of enrollment in the database.

- Calculation of HRT treatment duration and time since last exposure are based upon assumptions about actual use patterns because drug dispensing is all that can be directly observed using the HIRD.
- The study size is dependent on the rate of uptake of *Duavee* in the US. The study size projections are intentionally conservative (i.e., they are lower than Pfizer marketing forecasts of uptake in the US); to allow for adequate precision even if there is limited uptake in the first year following launch. Uptake will be evaluated at the end of Year 1 and, if needed, additional data sources or extension of study duration will be discussed in the 1st Interim Report.
- Sub analyses of prevalent users of unopposed estrogen may be difficult to interpret due to selection factors and unmeasured covariates. We anticipate that this group will include
 1. Patients with an intact uterus with past use of unopposed estrogen,
 2. Patients without a uterus for whom no hysterectomy was identified in the automated claims data due to timing of the procedure, and
 3. Patients who used both estrogen and sporadic progesterone for whom a progesterone dispensing was not observed.

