7.3.2. Endpoints

The study will identify non-fatal and fatal events of the following types:

- Primary endpoints:
 - Endometrial cancer;
 - Endometrial hyperplasia.
- Secondary endpoints:
 - Venous thromboembolism;
 - Coronary heart disease (defined as myocardial infarction [MI] and sudden death);
 - Stroke (including transient ischemic attack [TIA]);
 - Breast cancer;

- Ovarian cancer;
- Thyroid cancer;
- Renal cancer and adenoma;
- Gastrointestinal cancer;
- Any cancer (any malignant neoplasm);
- All-cause mortality.

All endpoints are included in the EU risk management plan (RMP) for CE/BZA (*Duavive*). Estrogen-associated cancers (breast, ovarian, endometrial cancers) and endometrial hyperplasia are important potential risks in the RMP based on the medical literature for HRT and background incidence rates (IRs) in postmenopausal women. An important identified risk potentially associated with *Duavee* use is VTE because it is a known safety concern for both of the individual component products of CE/BA (i.e., CE and BZA monotherapies). According to the literature,⁶ MI and stroke are important potential risks that are associated with the use of HRT products in general. Thyroid cancer, renal cancer, renal adenoma, and gastrointestinal tract cancers are considered as important potential risks based on their elevated background incidence in postmenopausal women. All cancers are included because of their inclusion in the EU RMP for CE/BZA. All-cause mortality is included to provide context to fatal occurrences of the safety endpoints. For example, if a finding of increased fatal stroke events is observed, it could be assessed if this result coincided with an increase in all-cause mortality.

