
Hypertension
	
401.xx-405.xx, 437.2x, V81.1x
	
CPT: 3077F, 3080F

Breast Pain
	
611.71
	

Diabetes
	
250.xx (Type 1: 250.x1, 250.x3; Type 2: 250.x0, 250.x2)
	

Renal Disease	403.01, 403.11, 403.91, 404.02, 404.03, 404.12, 404.13, 404.92, 404.93, 582.xx, 583.0x-583.7x, 585.xx, 586.xx, 588.0x, V42.0x, V45.1x, V56.xx	
Osteoarthritis	715.xx	
Osteoporosis	733.0x, V82.81	
Major Depression	296.2x, 296.3x, 311.xx, V79.0x	HCPCS: G8959, G8960, G8126, G8127, G9193-G9195, CPT: 3088F-3093F
History of VTE/CVA/CHD Event	415.1x, 451.11, 451.19, 451.2x, 451.81, 453.8, 414.xx, 430.xx-438.xx, V12.51-V12.54	
History of Breast, Ovarian, or Endometrial Malignancy	174.xx, 198.81, V10.3x, 198.6x, 183.0x, 236.2x, 182.0x, 198.82, V10.43, V10.42	19120, 58950-58954, 58956-58958, 58960

Family history of cancer	V16.xx	
Hysterectomy	V88.01, V88.02	ICD-9-CM procedure: 68.4x-68.7x CPT: 58150-58294

Potential Algorithms for Claims-Based Identification of Safety Endpoints*

Event	Algorithm
Endometrial Cancer	To be determined via validation
Endometrial Hyperplasia	To be determined via validation
Venous Thromboembolism	Hospitalization with any of the following ICD-9-CM diagnosis codes listed as the principal discharge diagnosis: 415.1x, 451.11, 451.19, 451.2x, 451.81, 453.8x
CHD (i.e. MI, fatal MI, and Sudden Death)	MI defined as a hospitalization with ICD-9-CM code 410.xx (excluding 410.x2) with either (1) a length of stay between 3 and 180 days or (2) discharge status indicating death if length of stay is less than 3 days.
Stroke/TIAs	Hospitalization with ICD-9-CM diagnosis codes 433.x1, 434.x1, 436.x, 437.x1, 437.9x with either (1) a length of stay between 3 and 180 days or (2) death if length of stay is less than 3 days, or hospitalization with a principal discharge diagnosis of 435.xx (TIA)
Breast Cancer	At least two outpatient or one inpatient ICD-9-CM diagnosis code(s) 174.xx.
Ovarian Cancer	At least two outpatient or one inpatient ICD-9-CM diagnosis code(s) 183.0x.

Thyroid Cancer	Thyroidectomy during follow-up and ≥ 2 ICD-9-CM 193.xx diagnosis codes recorded.
Renal Cancer	At least two outpatient or one inpatient ICD-9-CM diagnosis code(s) 189.x
Renal adenoma	At least two outpatient or one inpatient ICD-9-CM diagnosis code(s) 223.x
Gastrointestinal Tract Cancer	At least two outpatient or one inpatient ICD-9-CM diagnosis code(s) 150.x – 159.x

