All Cancers (Malignancies)	At least two outpatient or one inpatient ICD-9-CM diagnosis code(s) in the following range: 140.xx-208.xx

*Endpoints will be identified in the NDI based on the presence of applicable codes listed as cause of death.

Algorithms for Claims-Based Identification of Safety Endpoints Identified in the Literature

Event type	Algorithm	Study Population	Validation
CHD (MI, fatal MI and sudden death)	MI defined as a hospitalization with ICD-9-CM code 410.xx (excluding 410.x2) with either (1) a length of stay between 3 and 180 days or (2) death if length of stay is less than 3 days.	HIRD patients receiving COX-2 inhibitors	In HealthCore data, this had a PPV of 88.4% (83.2% - 92.5%), which was higher in patients receiving COX2-inhibitors (92.3 versus 84.2%). Previously reported PPV of 94% in Medicare data.

CHD (MI, fatal MI and sudden death)
	
At least one occurrence of any of the following codes: ICD-9 diagnosis codes: 410 - 414, 433 - 438, 440 - 441, 4439. ICD-9 procedure codes: 3601 - 3609, 361, 362, 3812, 3813, 3818, 3925, 3926, 3929, 3950, 3990 CPT codes: 33510 - 33545, 33572, 34101 - 34111, 34201 - 34203, 35301, 35311 - 35381, 35390, 35454 - 35456, 35459, 35470, 35473 - 35474, 35482 - 35483, 35485, 35492 - 35493, 35495, 35533, 35541 - 35571, 35641, 35646, 35654, 92975, 92980 - 92984, 92995 - 92996
 
*Note - this includes codes for angina, MI, CABG and other procedures not included in the study definition.
	
HIRD patients receiving statins
	
Sensitivity of 96%, specificity of 93% and Kappa of 0.82 (PPV not calculated).

Stroke/TIA
	
An algorithm using primary discharge diagnosis codes for acute ischemic or hemorrhagic stroke (International Classification of Diseases, Ninth Revision, Clinical Modification codes: 430, 431, 433.x1, 434.x1, 436).
	
Medicare patients
	
Positive predictive value of 92.6% (95% confidence interval, 88.8%-96.4%), a specificity of 99.8% (99.6%-99.9%), and a sensitivity of 59.5% (53.8%-65.1%). An algorithm using only acute ischemic stroke codes (433.x1, 434.x1, 436) had a positive predictive value of 91.1% (95% confidence interval, 86.6%-95.5%), a specificity of 99.8% (99.7%-99.9%), and a sensitivity of 58.6% (52.4%-64.7%).

[figure not shown]

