Stroke/TIA	Diagnosis codes for acute ischemic or hemorrhagic stroke (International Classification of Diseases, Ninth Revision, Clinical Modification codes: 430, 431, 433.x1, 434.x1, 436) in any position	Medicare data linked to Women's Health Initiative patients	Specificity was 99.7%, negative predictive value was 99.7%, sensitivity was 82.8%, positive predictive value was 85.8%, and $\kappa=0.84$. Whereas specificity and negative predictive value exceeded 99%, sensitivity ranged from 75% to 88% and positive predictive value ranged from 80% to 90% across stroke definitions.
Stroke/TIA	
Ischemic stroke without TIA: (1) Hospitalization with ICD-9-CM diagnosis codes 433.x1, 434.x1, 436.x, 437.x1, 437.9x with either (1) a length of stay between 3 and 180 days or (2) death if length of stay is less than 3 days.
 
(2) Hospitalization with ICD-9-CM diagnosis codes 433.x1, 434.x1 with either (1) a length of stay between 3 and 180 days or (2) death if length of stay is less than 3 days.
	HIRD patients receiving COX-2 inhibitors	
In HealthCore data, algorithm 1 had a PPV of 87.4%, and algorithm 2 95.5% based on review of 175 cases
 
A prior study of Medicare beneficiaries saw a PPV of 96% for algorithm 1.

Breast cancer	
At least one inpatient diagnostic or procedure code for breast cancer: Malignant neoplasm of female breast: 174.0-174.9 Any Incisional breast biopsy: 85.12 Excision or destruction of breast tissue: 85.20 - 85.25 Subcutaneous mastectomy: 85.33-85.36 Mastectomy: 85.41-85.48
	Piedmont cancer registry	The sensitivity of the algorithm was 76.7%, positive predictive value 87.9%.

Breast cancer	At least one claim with ICD-9-CM code 174.xx, 233.0, 238.3 or 239.3.	HealthCore	Not formally validated, however in this study 766 medical records were reviewed to stage breast cancer. Internal communication was that medical records were not excluded based on lack of evidence of breast cancer. 13.4% of cases were stage zero, and 10.3% could not be staged.

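### The high PPV credited to the stroke endpoint belongs to ischemic stroke without TIA; the protocol cites no validation for the TIA admissions it adds

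*Protocol*

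**What the plan says.** Section 7.3.2 defines the secondary endpoint as "Stroke (including transient ischemic attack [TIA"]) and calls stroke an important potential risk of HRT products in general.

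The candidate algorithm in Appendix 2 has two branches. The stroke branch is "Hospitalization with ICD-9-CM diagnosis codes 433.x1, 434.x1, 436.x, 437.x1, 437.9x with either (1) a length of stay between 3 and 180 days", or death if the stay is shorter. The TIA branch is "or hospitalization with a principal discharge diagnosis of 435.xx (TIA"), and the length-of-stay condition is not attached to it.

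Two statements describe how well the endpoint is supported. Section 7.9 says that "MI, and stroke endpoints have been confirmed to have a high PPV in HIRD validation studies". Section 7.3.2.2 names stroke among the endpoints for which validated algorithms were found; the tables concerned are in Appendix 2.

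The HIRD evidence in Appendix 2 is headed "Ischemic stroke without TIA: (1) Hospitalization with ICD-9-CM diagnosis codes 433.x1, 434.x1, 436.x, 437.x1, 437.9x", with the result "In HealthCore data, algorithm 1 had a PPV of 87.4%, and algorithm 2 95.5% based on review of 175 cases".

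Section 7.7.1 plans an IR and an adjusted HR for stroke, listed once. It adds that only the primary endpoints are validated in this project.

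**The concern.** A PPV is a property of a specific claims rule. If the rule is widened by a further diagnosis code, the published PPV no longer describes it unless the added code has been validated too. Here the rule is widened by TIA, and the statement of strength is carried over unchanged.

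What is at stake is how the stroke result is read. A reader who takes Section 7.9 at its word would treat an HR near 1 as coming from an endpoint of known, high validity. If many of the added admissions are not true events, and this is equally so in both cohorts, an HR near 1 is partly a product of misclassification.

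**Working it through.** **Step 1: set the rules side by side (Appendix 2).**

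| Source | Codes | 435.xx included? | PPV |
|---|---|---|---|
| Study candidate algorithm | 433.x1, 434.x1, 436.x, 437.x1, 437.9x, plus 435.xx | Yes | None given |
| HIRD, algorithm 1 | 433.x1, 434.x1, 436.x, 437.x1, 437.9x | No | 87.4% |
| HIRD, algorithm 2 | 433.x1, 434.x1 | No | 95.5% |
| Medicare, primary discharge diagnosis | 430, 431, 433.x1, 434.x1, 436 | No | 92.6% |
| Medicare, ischemic codes only | 433.x1, 434.x1, 436 | No | 91.1% |
| Medicare linked to the Women's Health Initiative, any position | 430, 431, 433.x1, 434.x1, 436 | No | 85.8% |

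The study rule is HIRD algorithm 1 plus 435.xx. The Medicare rows are filed under Stroke/TIA, but the first describes itself as "An algorithm using primary discharge diagnosis codes for acute ischemic or hemorrhagic stroke", and neither Medicare study lists a TIA code. This mismatch needs no assumption.

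**Step 2: check the stated PPV.** 153/175 = 87.43%, which rounds to the stated 87.4%. The exact binomial 95% CI is 81.6% to 92.0%. The numerator 153 is inferred, so this shows consistency only.

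**Step 3: PPV of the pooled endpoint.** Let t be the TIA share of counted events and p the PPV of a 435.xx admission. The protocol gives neither, so t = 20% to 50% and p = 70% to 50% are assumed.

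Pooled PPV = 0.874 × (1 − t) + p × t

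- t = 0.2, p = 0.7: 0.6992 + 0.1400 = 0.839
- t = 0.5, p = 0.5: 0.4370 + 0.2500 = 0.687

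**Step 4: effect on the HR.** Assume that false positives occur at the same rate in both cohorts, that true stroke and true TIA share the same HR, and that the PPV is the one in the E+P cohort. An HR of 1.5 is used for illustration.

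Observed HR = PPV × HR + (1 − PPV)

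- Validated rule alone: 0.874 × 1.5 + 0.126 = 1.437
- Pooled PPV 0.839: 0.839 × 1.5 + 0.161 = 1.420
- Pooled PPV 0.687: 0.687 × 1.5 + 0.313 = 1.344

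Adding TIA therefore costs about 0.02 to 0.09 on the HR. A further 0.06 (1.50 − 1.437) is already lost under the validated rule. At a true HR of 1.0 nothing is lost.

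**Step 5: a TIA effect that differs from the stroke effect.** Take perfect coding, t = 0.5 and a stroke HR of 1.5. If the TIA HR is 1.0, the pooled HR is 0.5 × 1.5 + 0.5 × 1.0 = 1.25. If the TIA HR is 2.0, it is 0.5 × 1.5 + 0.5 × 2.0 = 1.75. Pooling can move the HR in either direction.

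**The case against.** The sentence in Section 7.9 speaks of stroke, not of stroke and TIA, and for ischemic stroke it agrees with Appendix 2, which openly labels the evidence as excluding TIA. The algorithms are called candidate and potential, with final definitions still to come. Section 7.9 also lists outcome misclassification among the limitations. Pooling stroke with TIA is a legitimate choice for a secondary endpoint in a study aimed at estimation (Section 7.7.7). The shifts in the HR are small beside the precision expected: for scale only, the year-3 interval in Table 1 for endometrial hyperplasia at a true HR of 1.5 is 1.13 to 1.99.

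Most of this stands as a limit on the size of the point. It does not remove the mismatch: the endpoint that Section 7.3.2 defines includes TIA, and neither Section 7.9 nor Section 7.3.2.2 says that the validation does not extend to it. That the rule is provisional makes this a good time to correct the wording.

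A reader might also infer more than the protocol supports:

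- **That only a pooled HR will be reported.** The protocol describes no split, but the table shells in Annex 1 and any SAP are not at hand, so this cannot be asserted.
- **That pooling must bias the HR toward 1.** Step 5 shows that this holds for non-differential false positives, not for a TIA effect that differs from the stroke effect.
- **That leaving out PPV correction for secondary endpoints worsens the HR.** The correction described in Sections 7.7.1 and 7.7.4 multiplies case counts by a PPV. Applied equally to both cohorts, it leaves their ratio unchanged.
- **That the stroke conclusion should move to a stroke-only endpoint.** That would replace a prespecified endpoint, and nothing in the protocol requires it.

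**Conclusion.** The concern holds in a limited form. The confirmed PPV belongs to a narrower endpoint than the one defined, and the PPV of the pooled Stroke/TIA endpoint cannot be derived from the protocol. That conclusion rests on the text alone.

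The size is illustrative. It depends on an assumed TIA share, an assumed TIA PPV, an illustrative HR of 1.5, false positives equal in both cohorts, and the carry-over of 87.4% from the validated HIRD population, who were receiving COX-2 inhibitors. Under those assumptions a true HR of 1.5 appears as 1.42 to 1.34, against 1.44 for the validated rule. The point affects the reading of one secondary endpoint and one stated strength. The primary endpoints and the study size are untouched.

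**What to change.** - In Sections 7.9 and 7.3.2.2, limit the validation statements to ischemic stroke without TIA, and state that the 435.xx component has no cited validation.
- Keep the pooled Stroke/TIA endpoint as prespecified.
- In Section 7.7.1 or 7.7.4, add a supportive analysis of stroke without 435.xx under the validated rule. Report the IR, and the HR once the threshold in Section 7.7.6.2 is met (at least one event in each cohort and four in total). In this analysis a TIA admission should neither count as an event nor end follow-up.

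The cost is some wording and one further row from the same claims, with no chart review. The drawback is fewer events in the stroke-only row, so its HR may be imprecise or may not reach the threshold in early reports.
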